**Model (linear):**

**Change in KCCQ at 180 days = Intercept +  $\beta_1$ \*treatment +  $\beta_2$ \* baseline KCCQ +  $\beta_3$ \***

**baseline BB use**

**Hypothesis:**

**H0:  $\beta_1=0$**

**H1:  $\beta_1\neq 0$ .**

**The null hypothesis will be rejected if the p-value of the treatment effect is <0.05**

**Change in PGA at 180 days = Intercept +  $\beta_1$ \*treatment +  $\beta_2$ \* baseline PGA +  $\beta_3$ \* baseline**

**BB use**

**Hypothesis:**

**H0:  $\beta_1=0$**

**H1:  $\beta_1\neq 0$ .**

**The null hypothesis will be rejected if the p-value of the treatment effect is <0.05**

Missing values of 180 day heart rate, KCCQ and PGA will be imputed if missing values

---

 If events are rare, p-value from the Fisher's exact test will be reported.

exceed 10% of the observations (see section 12.5).

### 9.3 Tertiary Analyses

1. Beta-blocker use at 180 days as assessed by the (a) proportion of participants on a beta-blocker at 180-days, (b) proportion on target dose, (c) proportion of participants who are at  $\geq 50\%$  target dose (d) the proportion discontinuing beta-blockers at 180 days and (e) the mean change in beta-blocker dose from discharge to 180 days will be compared between the randomization arms. - The mean change of beta-blocker dose will be calculated for participants who provide data at baseline and at 180 days post-discharge visits.

The proportions of participants on beta-blocker, the proportions on target dose, the proportion on at least 50% of the target dose, and the proportions discontinuing beta-blocker at 180 days will be summarized by randomization arms and tested using the Chi-square test. The change in beta-blocker dose from discharge to 180 days will be summarized and compared using the Wilcoxon rank sum test.

2. Ivabradine use at 180 days as assessed by the (a) proportion of appropriate participants with any initiation of ivabradine at 180 days, (b) the proportion of appropriate participants at the maximum dose of ivabradine at 180 day (i.e., 7.5 mg

---

 Comparing the mean change in beta-blocker dose is interpreted as comparing the distribution of dose changes between the randomization arms.

twice daily), and (c) the mean dose of ivabradine achieved at 180 days will be compared between the randomization arms.

Participants who do not provide the 180 day visit data will be coded as failures (ivabradine=0 and dosage=0.0). The mean dose of ivabradine achieved will be calculated for participants who provide data at 180 days post-discharge visit and using imputed values for the participants who do not provide 180 day visit data. As a sensitivity analysis, data will also be analyzed on observed data without imputing missing values. In addition, ivabradine dosage will be summarized for participants on ivabradine at the 180 day visit.

The proportions of appropriate participants with any initiation of ivabradine and the proportion of appropriate participants at the maximum dose of ivabradine at 180 days will be summarized as incidences by the randomization arms and tested using the Chi-Square test. The dose of ivabradine achieved at 180 days will be summarized and compared using the Wilcoxon rank sum test.

3. The event incidences for the following adverse events will be summarized by the randomization arms.
  - a. Symptomatic bradycardia
  - b. Symptomatic hypotension
  - c. Other symptoms leading to ivabradine discontinuation

Other symptoms leading to ivabradine discontinuation will be determined using data collected in the AE CRF panel. .

Differences between the randomization arms of the events will be tested using the Chi-square test.

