## **9 ENDPOINT ANALYSES**

### **9.1 Primary Analysis**

The primary analysis will be performed on an intention-to-treat (ITT) basis including all randomized participants. Participant who are not assessed at the 180 day visit due to death or other reasons of early termination, and otherwise medication data not being collected will be coded as failures (ivabradine use=0). The primary analysis will be based on the imputed data. For sensitivity analysis, observed ivabradine use will be used. Given that death is a competing risk of ivabradine use, a competing risk analysis will be performed (see section 11).

The primary analysis will be performed with a logistic regression model, with ivabradine use at 180 days as the binary outcome variable and indicator variables for treatment group main effects

---

 Ivabradine use will be determined from the Ivabradine use pane and will be coded as a “0/1” (no/yes) variable.

and category (0/1) of baseline beta-blocker (BB) use. The treatment effect for the ivabradine at discharge group will be summarized by the odds ratio and associated 95% confidence interval.

Ivabradine use in the ivabradine arm at 180 days is expected to be higher than in the usual care arm.

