## **9.2 Secondary Analyses**

### **1. Heart Rate Assessments**

- a. Change in heart rate from baseline to 180 days will be compared across randomization groups. Change will be calculated as follows: (Baseline heart rate – 180 day heart rate). Comparisons across randomization groups will be performed using a linear model with adjustment for baseline heart rate and beta-blocker use. Randomization groups will be included in the regression model as main effect.

---

 Baseline beta-blocker use will be coded as a “0/1” variable with participants who received beta-blocker coded as “1” and those who did not receive beta-blocker as “0”.

 All change from baseline results presented are calculated similarly.

Heart rate is expected to be lower in the ivabradine arm than the usual care arm.  
Thus, change from baseline is expected to be higher in the ivabradine arm.

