### 5. Beta-blocker (BB) use

Beta-blocker use measures were obtained from the current medication (CM) data

Baseline BB use at baseline = CM.CMBB =1 where VISITID=10).

a) BB use at 180 days = CM.CMBB=1 (where VISITID=50)

b) Proportion on target dose at 180 days (doses were calculated based on Carvedilol equivalent basis).

If VISITN =50 and Carvedilol equivalent dose = 50 mg then on target dose=1 (yes); else if Carvedilol equivalent dose is not missing on target dose=0(no).

c) Proportion on 50 % of target dose (Carvedilol equivalent) at 180 days.

If Carvedilol equivalent dose is at least 25 mg then on 50% target dose=1; else if Carvedilol equivalent dose is not missing on 50% target dose =0.

d) Proportion of participants discontinuing (No beta-blocker use at 180 days in those who used it during an early visit)

e) Mean change in dose (Carvedilol equivalent)

Change in dose from baseline to 180 days (converted to Carvedilol equivalent dose) = CM.CMBBDS (where VISITID=10) – CM. CMBBDS (where VISITID=50)

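### Three day-180 beta-blocker proportions and the dose change are tested without the baseline value the trial already collects; the tests are valid but lose precision if day-180 status tracks baseline

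*SAP*

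**What the plan says.** SAP 9.3 item 1 lists five comparisons: (a) on a beta-blocker at day 180, (b) on target dose, (c) on at least 50% of target dose, (d) discontinuing, and (e) change in dose. One sentence sets the test for all four proportions; its closing words are "the proportions discontinuing beta-blocker at 180 days will be summarized by randomization arms and tested using the Chi-square test". For (e): "The change in beta-blocker dose from discharge to 180 days will be summarized and compared using the Wilcoxon rank sum test". No covariate is named for any of them. Protocol 10.4 says only that these endpoints are compared between groups, so the choice of method was left to the SAP.

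The baseline value is available. SAP Appendix 1 item 5 derives it from the medication data: "Baseline BB use at baseline = CM.CMBB =1 where VISITID=10". The same item computes (e) as "Change in dose from baseline to 180 days (converted to Carvedilol equivalent dose", which needs a baseline dose, and defines (d) as "No beta-blocker use at 180 days in those who used it during an early visit".

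Elsewhere the SAP uses baseline beta-blocker use as a covariate. The primary logistic model in 9.1 has indicators for treatment "and category (0/1) of baseline beta-blocker (BB) use". The linear models in 9.2 for change in heart rate, heart rate at day 180, KCCQ and PGA include it as well. Section 6 also sends dose data through the Appendix 2 mixed model, whose terms are treatment, time and their interaction.

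**The concern.** Baseline beta-blocker status is used to adjust ivabradine use, heart rate and quality of life, but not the outcomes that are the same quantity measured later. Change in heart rate and change in KCCQ are each adjusted for their own baseline; change in beta-blocker dose is not.

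There is reason to expect tracking. Protocol 3.2 requires maximally tolerated beta-blocker doses at entry (or intolerance), and 3.3 excludes a documented plan to up-titrate within 4 weeks. Randomization is stratified by site only, so the design does not balance beta-blocker dose, and SAP 2.3 records that enrolment stopped at 104.

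At stake is the precision of a tertiary comparison: the effect of the strategy on evidence-based implementation of beta-blockers.

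**Working it through.** **The plan's own figure.** The documents give no power or precision figure for the beta-blocker endpoints. The one stated power for a proportion, in Protocol 10.2 (35% v 50%, two-sided 0.05, 85%, continuity-corrected chi-square, 8% missing), reproduces. The uncorrected n is [1.96·√(2·0.425·0.575) + 1.036·√(0.35·0.65 + 0.50·0.50)]² / 0.15² = 193.5 per arm. The continuity correction gives 207 per arm, or 414, and 414/0.92 = 450. It does not bear on these endpoints.

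**Inputs.** From the documents: 104 enrolled, 1:1, hence 52 per arm; two-sided 0.05. Everything else is assumed: baseline prevalence π, the control-arm day-180 probability p₁ in those positive at baseline and p₀ in those negative, and the effect size. All 104 are treated as analysed, which is optimistic, since SAP 13.5 expects more than 10% missing at day 180 for the secondary endpoints.

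**Proportions (a) to (c).** The control-arm correlation is φ = (p₁ − p₀)·√[π(1−π) / p̄(1−p̄)], with p̄ = πp₁ + (1−π)p₀. The unadjusted difference should have about 1/(1−φ²) times the variance of the stratified one. For target dose with π = 0.40:

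- weak tracking (55% v 30%): φ = 0.25, ratio 1/(1−0.0625) = 1.07
- moderate tracking (70% v 20%): φ = 0.50, ratio 1/(1−0.25) = 1.33
- strong tracking (80% v 15%): φ = 0.65, ratio 1/(1−0.42) = 1.72

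Simulated power at 52 per arm, chi-square against Mantel-Haenszel stratified by baseline status. Where two figures appear, the effect was set once as a constant risk difference and once as a constant odds ratio.

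| Endpoint and assumption | Effect | Chi-square | Stratified | Variance ratio |
|---|---|---|---|---|
| Use; 90% at baseline, 95% persist, 30% start | −10 points | 27–28% | 36–37% | 1.4–1.6 |
| Use; 80% at baseline, 90% persist, 30% start | −10 points | 22% | 27–28% | 1.4–1.5 |
| Target dose, weak tracking | +20 points | 57–58% | 55–56% | 1.06 |
| Target dose, moderate tracking | +20 points | 57–58% | 64–65% | 1.3 |
| Target dose, strong tracking | +15 points | 37% | 49–51% | 1.6–1.7 |

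Under the null, rejection rates were about 4.6% to 6.0% for the chi-square and 4.5% to 5.0% for the stratified test.

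**Chance imbalance.** The standard deviation of the between-arm difference in a baseline share is √[2π(1−π)/52]: 5.9 points at π = 0.90, 7.8 at 0.80 and 9.6 at 0.40. In the simulations about 0.60 to 0.65 of an imbalance in use carried into the unadjusted day-180 difference in use. For target dose the share was 0.25, 0.50 and 0.65 under weak, moderate and strong tracking. The unadjusted standard error already contains this variation; stratifying removes it.

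**Dose change (e).** With equal variances at both times and correlation r, the variance of a mean change score is proportional to 2(1−r) and that of ANCOVA to 1−r². The ratio is (1+r)/2:

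- r = 0.5: 0.75, so 104 participants analysed by change score are worth 104 × 0.75 = 78 with ANCOVA
- r = 0.7: 0.85, worth 88
- r = 0.9: 0.95, worth 99

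This compares ANCOVA with a mean change score, not with the planned Wilcoxon test, so it indicates the size of the gain only. It also runs the other way from (a) to (c): close tracking enlarges the gain for the proportions and shrinks it for the dose change.

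**The case against.** The case for leaving the plan alone has several sound parts.

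- **It is a tiered plan.** SAP 13.2 sets chi-square for binomial outcomes and Wilcoxon for continuous ones as the general rule. The secondary endpoint of heart rate below 70 bpm, the ivabradine proportions, tolerability and clinical events are all unadjusted chi-square tests too. This stands: the choice is not an oversight peculiar to beta-blockers. It does not remove the precision gain.
- **Two of the five endpoints already use earlier data.** A reader might infer from the quoted sentence that no beta-blocker endpoint takes account of earlier use. Appendix 1 does not support that: discontinuation is limited to earlier users, so imbalance in baseline use largely cannot enter, and dose change subtracts the baseline dose. For (e), only the inefficiency of fixing the baseline slope at 1 remains.
- **Wilcoxon is not the only dose analysis.** The section 6 mixed model compares slopes and the arms at day 180. But baseline enters it as an outcome, not as a covariate, so it is not the adjusted comparison.
- **The gain is uncertain and may not rescue the comparison.** For a 10-point effect at 50% prevalence, SE = √(2·0.25/52) = 0.098, and power is about 18% unadjusted against 19%, 22% and 30% at correlations 0.3, 0.5 and 0.7. That is low either way.
- **Unblinding has occurred.** Addendum 2 records a decision taken after database lock and unblinding, so replacing a prespecified test now would be post hoc. This governs labelling and argues for keeping the planned tests.

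**Conclusion.** The point holds as a matter of efficiency for (a), (b) and (c), and more weakly for (e). At 52 per arm, with the effect on the odds-ratio scale, the gain for target dose is about 7 points of power under moderate tracking (57% to 64%, 20-point effect) and 12 under strong tracking (37% to 49%, 15-point effect); it is nil under weak tracking. For dose change the variance saving is 25%, 15% and 5% at r = 0.5, 0.7 and 0.9, measured against a mean change score. All of this rests on assumed prevalences, tracking and effect sizes.

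Three stronger readings are not supported. The unadjusted tests are not invalid: randomization protects the type I error, and the simulations agree. Chance imbalance is not an extra error on top of the reported interval. And the documents do not state an objective of testing whether ivabradine displaces beta-blockers; Protocol 2.3 and SAP 2.2.3 speak of exploring evidence-based implementation of both drugs.

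The stakes are low: these are tertiary endpoints, with no multiplicity adjustment, in a trial that stopped at 104.

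**What to change.** In SAP 9.3 item 1:

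- For (a) to (c), add a Mantel-Haenszel test stratified by, or a logistic model adjusted for, the baseline value of the same measure: baseline use for (a), baseline carvedilol-equivalent dose category for (b) and (c). State that Mantel-Haenszel is the default when any baseline-by-arm cell is sparse, and fix what counts as sparse.
- For (e), add a rank-based or linear ANCOVA of day-180 dose on arm and baseline dose.
- Leave (d) as it is.
- Keep the crude percentages and the planned chi-square and Wilcoxon tests alongside.
- If the adjusted analyses are added after unblinding, label them post hoc. SAP 13.6 calculates no p-values for exploratory analyses, so if they are classed that way, report estimates and intervals only.

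The cost is SAP wording and a few lines of code, with no new data. The drawback is (a): if nearly everyone takes a beta-blocker at baseline, the non-user stratum is small, a logistic model may be unstable, and the yes/no indicator carries little information.

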### 2.5.3 Tertiary endpoints

Tertiary endpoints are

- 1) Beta-blocker use at 180 days as assessed by the:
  - a) Proportion of participants on beta-blocker at 180 days
  - b) Proportion on target dose
  - c) Proportion discontinuing beta-blockers at 180 days and
  - d.) Mean change in beta-blocker dose from discharge to 180 days.
- 2). Ivabradine use at 180 days as assessed by the:
  - a) Proportion of appropriate participants with any initiation of ivabradine at 180 days
  - b) Proportion of appropriate participants at the maximum dose of ivabradine at 180 day.
  - c) Mean dose of ivabradine achieved at 180 days.
- 3). Tolerability of ivabradine and events of interest:
  - a) Symptomatic bradycardia
  - b) Symptomatic hypotension
  - c) Other symptoms leading to ivabradine discontinuation
- 4). Summary of barriers to acquisition of ivabradine

---

 Beta-blocker target dose is defined as participants who receive Carvedilol equivalent total daily dose of 50 mg

 Appropriate participants are defined as participants who have a sinus rhythm (participants excluding those with AF) and heart rate of  $\geq 70$  bpm. For participants missing 180 day ECG, results from the baseline ECG are used to determine appropriateness.

 Receiving ivabradine at any time point during the study.

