### **13.5 Handling of Missing Data**

All efforts will be made to make sure all data needed for the analyses outlined in the SAP are complete. However, it is possible that some data will be missing. Missing data is a common problem in clinical research. It reduces statistical power (the probability that the test will reject the null hypothesis when it is false) and results in biased parameter estimates (Kang, 2013). Outcomes for participants who do not provide data during the 180 day visit will be imputed as failures. Missing heart rate, PGA and KCCQ values will be imputed for the final (180 day) visit using multiple imputation technique if more than 10% of the measures are missing.

It is expected that missing 180 day visit values constitute > 10% of the secondary endpoints (Heart rate, KCCQ and PGA). Thus, multiple imputation (MI) will be performed and presented for the ITT and Treated populations, respectively.

Imputation will be conducted using PROC MI and imputed data analyzed with PROC MIANALYZE in SAS 9.4.

The following variables shall be used in the imputation:

AGE, SEX, RACE, ETHNICITY, WEIGHT, NYHA class, LVEF, and baseline value of the imputed variable) – For NYHA class, WEIGHT and LVEF, baseline values will be used.

RACE shall be recoded to: White, Black and Others (combining American Indian, other, and mixed - as they are of very low frequency)

Results of the imputation shall be presented as the primary result of the secondary endpoints. A total of 25 imputations will be conducted for each imputed value.

Sensitivity analyses will be conducted by analyzing these endpoints with and without imputation.

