### Data Sources for Endpoints

#### 1. Ivabradine use

a) Ivabradine use (1/0) at 180 days comes from either the current medications data (CM) or the ivabradine usage data (DRG).

If CM.CMIVA=1 and VISITID=50 or DRG.DRIVA=1 and VISITID=50. If missing then it is imputed to 0. (Note: analysis will also be done without imputation).

b) Ivabradine dose change from baseline to 180 days

Ivabradine use and dose at baseline comes from the ivabradine initiation in hospital (EXH) data EXH.EXRECH (use) and EXH.EXLDH (dose) EXH.EXRECH (use) and EXH.EXLDH (dose) (VISITID=10) and ivabradine obtaining the first time (outpatient) (EX) EX.EXREC and EX.EXPDOS (VISITID=60 study wide to be merged in)

For other time points use the ivabradine usage data DRG.DRIVA (use) DRG.DRDSG (dose). Missing doses will be imputed to 0. (Note: analysis will also be done without imputation).

Dose change from baseline to 180 days = EXH.EXLDH, EX.EXDOS (VISITID=10)-DRG.DRDSG (where VISITID=50)

c) Proportion with any initiation

If participant received ivabradine at any time during the visits

If EXH.EXRECH=1 or EX.EXREC=1 or CM.CMIVA=1 or DRG.DRIVA=1 at any visit then ANYIVA=1 else ANYIVA=0; (Note: No imputation of missing ivabradine use occurs for this derivation)

d) Proportion on maximum dose at 180 days

Use ivabradine usage data

If DRG.DRSG =15 (mg) and VISITID=50 then on ivabradine maximum dose=1; else if DRG.DRSG not missing on ivabradine maximum dose=0.

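### SAP 9.3 does not exempt any initiation from its day-180 failure coding, which conflicts with Appendix 1(c) and leaves the rule for tertiary endpoint 2(a) unresolved

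*SAP*

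**What the plan says.** Four places in the SAP bear on tertiary endpoint 2(a).

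- **9.3, item 2.** The item opens with "Ivabradine use at 180 days as assessed by the (a) proportion of appropriate participants with any initiation of ivabradine at 180 days" and goes on to (b) maximum dose and (c) mean dose. The next paragraph begins: "Participants who do not provide the 180 day visit data will be coded as failures (ivabradine=0 and dosage=0.0". It exempts none of the three. The sentence after it concerns mean dose only. An observed-data analysis is added for sensitivity: "As a sensitivity analysis, data will also be analyzed on observed data without imputing missing values". Measures (a) and (b) are tested by chi-square.
- **2.5.3, footnote 3.** Any initiation is defined as "Receiving ivabradine at any time point during the study".
- **Appendix 1, item 1(c).** The derivation is "If EXH.EXRECH=1 or EX.EXREC=1 or CM.CMIVA=1 or DRG.DRIVA=1 at any visit then ANYIVA=1 else ANYIVA=0", with the remark "Note: No imputation of missing ivabradine use occurs for this derivation". Items 1(a) and 1(b), on day-180 use and on dose, do set missing values to 0.
- **13.5.** The general rule is "Outcomes for participants who do not provide data during the 180 day visit will be imputed as failures". Heart rate, PGA and KCCQ then go to multiple imputation. No exception is made for any initiation.

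No text says whether the body of the SAP or Appendix 1 governs.

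**The concern.** Coding a missing day-180 visit as failure is a defensible convention for use at day 180, because a participant who has died or disappeared is not known to be taking the drug. It does not suit an ever/never measure. A start recorded in hospital or at an early visit is a known fact, and a later absence cannot cancel it.

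Taken literally, 9.3 would overwrite that fact for every documented starter without day-180 data. In-hospital starting is the assigned strategy in one arm only, so more of the overwritten records would be expected there. Initiation in the pre-discharge arm, and probably the contrast between arms, would be understated. Getting patients started on the drug is one of the things this trial set out to study. A programmer following 9.3 and one following Appendix 1(c) could report different results for the same tested endpoint, each with SAP text in support.

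**Working it through.** **1. The rules on example records.**

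| Record | Appendix 1(c) | 9.3 read literally | 9.3 read narrowly (only the day-180 field set to 0, then 1(c) applied) |
|---|---|---|---|
| In-hospital start, use at an early visit, no day-180 data | 1 | 0 | 1 |
| Never started, no day-180 data | 0 | 0 | 0 |
| In-hospital start, on drug at day 180 | 1 | 1 | 1 |

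The literal rule departs from Appendix 1(c) only for documented starters without day-180 data. The narrow rule never departs from it.

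**2. Inputs for the size.** The plan gives no figure for any initiation, so there is none to reproduce. Its 35% and 50% (protocol 10.2) are assumed rates of use at day 180, not of ever starting. The illustration uses:

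- ever-start rates s of 90% v 35% and 70% v 35%, all assumed;
- a share m without day-180 data of 10% and 20%, assumed equal in both arms and unrelated to starting. SAP 13.5 expects more than 10% missing for heart rate, KCCQ and PGA;
- 104 enrolled (SAP 2.3), taken as 52 per arm under 1:1 allocation;
- every participant counted as appropriate.

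**3. Formulae.** Appendix 1(c) reports s and literal 9.3 reports s(1 − m). The difference is therefore (s₁ − s₂)(1 − m), and the number of starters recoded per arm is 52·s·m.

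| s₁ v s₂ | m | Appendix 1(c) difference | Literal 9.3 rates | Literal 9.3 difference | Starters recoded |
|---|---|---|---|---|---|
| 90% v 35% | 10% | 55 | 81.0% v 31.5% | 49.5 | 4.7 v 1.8 |
| 90% v 35% | 20% | 55 | 72.0% v 28.0% | 44.0 | 9.4 v 3.6 |
| 70% v 35% | 10% | 35 | 63.0% v 31.5% | 31.5 | 3.6 v 1.8 |
| 70% v 35% | 20% | 35 | 56.0% v 28.0% | 28.0 | 7.3 v 3.6 |

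Differences are in percentage points. The loss is 5.5 and 11 points in the first scenario and 3.5 and 7 in the second. Under the narrow reading it is zero throughout.

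**4. Effect on the test.** With 52 per arm and 70% v 35%, power of the uncorrected two-proportion test is 95.8% under Appendix 1(c), against 90.7% and 83.5% under literal 9.3 at m of 10% and 20%. With 90% v 35% it stays at 99.8% or above. In these scenarios the estimate suffers more than the test.

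**5. Unequal missingness.** If m differs by arm, the loss in the difference is s₁m₁ − s₂m₂. It stays positive unless m₂/m₁ exceeds s₁/s₂, that is 0.90/0.35 = 2.6 or 0.70/0.35 = 2.0.

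**6. Denominator.** SAP 2.5.3, footnote 2, states: "For participants missing 180 day ECG, results from the baseline ECG are used to determine appropriateness". Entry required sinus rhythm and a heart rate of at least 70 bpm. Nearly all participants without a day-180 ECG therefore stay in the denominator, so a recoded starter would count there as a non-initiator.

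**The case against.** The best answer is that the passages can be reconciled. The two zeros in 9.3 can be taken as the day-180 use and dose fields, which Appendix 1(a) and 1(b) also set to 0 when missing. Any initiation is a different variable, built as an OR across visits, and a zero at day 180 cannot undo a one recorded earlier. Appendix 1(c) and footnote 3 are specific to this endpoint and agree with each other, and a programmer would normally prefer them to a shared sentence. This reading is reasonable. It means that nobody can infer from the SAP that starters were in fact recoded. It does not remove the defect, because 9.3 places the failure rule directly after (a) to (c), does not limit it to day-180 fields, and does not refer to Appendix 1(c).

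A reader might also take 13.5 to impose failure coding on every outcome. The text does not support that. The sentence is unqualified but does not claim to cover all outcomes, and the next one sends three measures to multiple imputation. Beta-blocker dose change in 9.3 uses only participants with data at both visits, and Appendix 1 sets clinical events to 0 for anyone assessed at any time. What remains is that 13.5 makes no exception for any initiation.

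Nor should the 90% scenario be read as the plan's expectation. The drug was not supplied, in-hospital dosing was to happen if possible, and inability to pay was foreseen. Hence the lower scenario alongside it.

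The observed-data sensitivity analysis does not settle the matter, since it leaves the main result for 2(a) undefined.

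**Conclusion.** The point stands as an unresolved conflict between two instructions for one tested endpoint. On its plain reading 9.3 turns documented starters without day-180 data into non-initiators, while footnote 3 and Appendix 1(c) keep them as initiators.

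The cost ranges from zero under the narrow reading to 3.5–11 percentage points of between-arm difference under the literal one. That range assumes ever-start rates of 90% or 70% v 35%, 10–20% missing equally in both arms and unrelated to starting, and all participants counted as appropriate. The documents support none of these ever-start rates directly.

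The documents do not show which rule was programmed, so they do not support a claim that a reported initiation rate is wrong. The primary endpoint is unaffected: failure coding under 9.1 fits use at day 180. This is one part of a tertiary, exploratory endpoint, and the correction is minor.

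**What to change.** 1. In 9.3, item 2, limit failure coding to day-180 use and day-180 dose, that is to 2(b) and 2(c).
2. State there that 2(a) follows Appendix 1(c), using all EXH, EX, CM and DRG records at any visit, with no failure coding.
3. Put the same limit and exception in 13.5.
4. Align Appendix 1(d) with 9.3. Item 1(d) assigns 0 for maximum dose only when the day-180 dose is present, so a missing dose stays unclassified, whereas 9.3 codes it as 0.
5. State which rule produced the any-initiation result. Addendum 2 shows that the database is locked and treatment unblinded, so this would be a post-unblinding clarification and should be labelled as one.

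The cost is a few sentences, issued as a supplement or amendment as SAP section 1 provides. If the literal rule was programmed, the 2(a) summary and its chi-square test must also be rerun. If 1(d) was applied as written, the 2(b) table may change too. No new data are needed.
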